### 5.2.5.3 Suicidal risk assessed by the C-SSRS

The C-SSRS®, developed by leading experts in cooperation with the FDA, is a questionnaire assessing both suicidal behaviour and suicidal ideation. The medical qualified clinician administered interview with the questionnaire has a typical administration time of five minutes, can be easily coupled with evaluation of inclusion/exclusion criteria and causes only a low burden on patients and the assessing medical qualified clinician. The interview consists of five questions related to suicidal behaviour and five questions related to suicidal ideation, evaluated as either present or not. Patients presenting with any suicidal behaviour or suicidal ideation will be excluded from participation in the trial. The C-SSRS® has been widely used in large multinational clinical trials in the past four years and it is available in over 20 languages. The C-SSRS® will be administered by the medical qualified clinician or expert clinician and will be assessed at the screening visit with the aim to exclude patients with active moderate or severe symptomatology prior to the Screen Visit, or recent (or current) suicidal or suicide attempt according to the C-SSRS® (baseline/screening version). Subsequently, the C-SSRS® “since last visit” assessment will be performed at each clinic visit after visit 3 and as shown in the [Flow Chart](#). If there is a positive response of suicide attempt or suicidal ideation by the patient during the administration of the C-SSRS® during the treatment period, the medical qualified clinician is to immediately interview the patient during the clinic visit and determine if the patient will be discontinued from the trial and appropriate actions for the patient’s safety have to be initiated by the investigator. For assessment of the C-SSRS® paper forms will be used and results will be transcribed into the e-CRF.

■      ■

■      ■

■

■

■

Proprietary confidential information.

© 2017 Boehringer Ingelheim International GmbH or one or more of its affiliated companies. All rights reserved.

This document may not - in full or in part - be passed on, reproduced, published or otherwise used without prior written permission.

[REDACTED]

## 6. INVESTIGATIONAL PLAN

### 6.1 VISIT SCHEDULE

All trial visits should preferentially take place in the morning starting before 9:00 AM. Patients should be instructed not take trial medication on the morning of a clinic visit before attending the clinic.

All patients are to adhere to the visit schedule as specified in the [Flow Chart](#) (with time window for rescheduling).

If any visit has to be rescheduled, subsequent visits should follow the original visit date schedule. The trial medication packs contain sufficient medication to allow for these time windows.

The end of the trial is defined as “last patient out”, i.e. last visit completed by the last patient.

If the reason for removal of a patient from the treatment is an adverse event or an abnormal laboratory test result, the patient must be followed until complete resolution or stabilization of the event or until follow-up is agreed adequate by the Investigator and BI Clinical Monitor.

### 6.2 DETAILS OF TRIAL PROCEDURES AT SELECTED VISITS

Study procedures to be performed at each visit are listed in the [Flow Chart](#). Additional details regarding visit procedures are provided below.

The following section describes recommendations for the conduct of the neuropsychological assessments.

- The assessments should be administered in the same sequence found in the flowchart and approximately at the same time of the day at every applicable visit.
- Assessment of the Neuropsychological Rating Scales should preferentially be done by the same member of the site staff for a given patient throughout the study period.
- It is strongly recommended that a member only performs independent tests (meaning that different assessments of cognition should be performed by different members of the team). The study partner contributing to the functional assessments should not change during the study. If that cannot be avoided this is to be recorded in the source data and as a protocol violation.
- The adverse events should be evaluated by a team member that is not directly involved in the neuropsychological and functional assessments (NTB, CDR, , ADCS-ADL and ADAS-cog11) to prevent partial unblinding.

The members of the site staff performing the assessment have to be properly trained (either at the investigator training or individually) and training documentation has to be filed in the ISF. The training standards and standards for the conduct of the assessments will be defined for each assessment individually and can be found in the ISF. It is the responsibility of the

**Proprietary confidential information.**

© 2017 Boehringer Ingelheim International GmbH or one or more of its affiliated companies. All rights reserved.

This document may not - in full or in part - be passed on, reproduced, published or otherwise used without prior written permission.

Principal Investigator at the site to ensure proper training of all members of the site staff involved in the neuropsychological assessments.

This trial (1289.7) investigates patients with mild Alzheimer's dementia. In parallel BI is investigating the effect of BI 409306 in patients with cognitive impairment caused by the Alzheimer's disease in study 1289.5. It is expected that both trials share a high percentage of trial sites. One of the medically well-established non-invasive neurological assessments is the Mini Mental Stage Examination (MMSE) which evaluates the severity of cognitive impairment. This assessment is used in both trials as part of the eligibility assessments.

Patients who do not reach the required scores of  $<27$  in MMSE or CDR total score of greater than 1 are not eligible for this study and must be registered as screen failure in IRT. If the result of the MMSE and CDR would fulfill the requirements of the parallel trial 1289.5 and the patient and his study partner agree to alternatively participate in 1289.5 after giving a new consent then the results of the MMSE and CDR can be transferred into the database of 1289.5 without repeated performance of the MMSE and CDR and vice versa. This prevents the risk of unwanted learning effects which would be a consequence of repeating the MMSE and CDR in the same patient. This rule only applies if the screening visit for 1289.5 is no later than 7 days after the MMSE for 1289.7 was performed. The patient will then be registered as a new patient in the IRT of 1289.5. This does not apply to sites participating in only one of the 1289.5/1289.7 studies.

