## CLINICAL TRIAL PROTOCOL SYNOPSIS

Name of company: Boehringer Ingelheim		Tabulated Trial Protocol	
Name of finished product: NA			
Name of active ingredient: BI 409306			
Protocol date: 17 Oct 2014	Trial number: 1289.7		Revision date: 23 Feb 2017
Title of trial:	A multi-centre, double-blind, parallel-group, randomised controlled study to investigate efficacy, safety and tolerability of orally administered BI 409306 during a 12-week treatment period compared to placebo in patients with cognitive impairment due to Alzheimer's Disease		
Co-ordinating Investigator:	[REDACTED]		
	Phone: [REDACTED] Fax: [REDACTED]		
Trial site(s):	60		
Clinical phase:	II		
Objective(s):	To assess safety, tolerability and efficacy of different doses of BI 409306 compared to placebo in treatment of cognitive impairment due to AD		
Methodology:	Placebo -controlled, double-blind, randomised parallel-design comparison of 5 groups over 12 weeks of treatment.		
No. of patients:	total entered: 354 each treatment: 118 for placebo group and 59 for each treatment group		
Diagnosis :	Patients with diagnosis of mild Alzheimer's dementia according to the recommendations from the National Institute on Aging-Alzheimer's Association workgroups on diagnostic guidelines for Alzheimer's disease and ICD10 and DSM V criteria		
Main criteria for inclusion:	The population will include male and female patients at least 55 years old with mild Alzheimer's dementia. A MMSE (Mini-Mental-State-Examination) score between 18-26, an ADAS-cog 11 score higher than 12 at screening, and a global CDR score of 1 or greater are required for inclusion. A caregiver has to be available for study site activities and on call by arrangement with the study site.		
Test product(s):	BI 409306		
dose:	10mg QD, 25mg QD, 50mg QD, 25mg BID		
mode of admin.:	Tablet, Oral		

Proprietary confidential information.

© 2017 Boehringer Ingelheim International GmbH or one or more of its affiliated companies. All rights reserved.

This document may not - in full or in part - be passed on, reproduced, published or otherwise used without prior written permission.

Name of company: Boehringer Ingelheim		Tabulated Trial Protocol	
Name of finished product: NA			
Name of active ingredient: BI 409306			

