### 3.3 SELECTION OF TRIAL POPULATION

Untreated male and female patients, at least 55 years old, with diagnosis of mild Dementia of Alzheimers' Type (DAT) will be randomised. Recruitment will be competitive and participating sites are expected to enter at least **354** patients.

Patients who fail to complete all assessments in terms of primary and secondary endpoints according to the study protocol will not be considered study completers (see [Sections 6.2](#) and [7.3](#) for details). Patients who discontinue following randomisation may not be re-enrolled at a later date. A record is kept of all patients failing to complete all trial visits and their reasons for discontinuation. Re-screening of not yet randomised patients can be allowed in exceptional cases but should be discussed on a case-by-case basis between the study site, Monitor staff and with the TCM.

Permission to randomise more than 15 patients per site must be obtained from the TCM at Boehringer Ingelheim. This will only be allowed after a careful review of the enrolment status.

A log of all patients included into the study (i.e. having given informed consent) will be maintained in the ISF at the investigational site irrespective of whether they have been treated with investigational drug or not.

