### 3.3.2 Inclusion criteria

Patients are included in this study if they meet all of the following criteria:

1. Diagnosis of mild Alzheimer's Dementia according to the recommendations from the National Institute on Aging-Alzheimer's Association workgroups on diagnostic guidelines for Alzheimer's disease (see [section 3.3.1](#)).
2. Mini-Mental State Examination (MMSE) score of 18-26, an Alzheimer's Disease Assessment Scale – cognitive subscale (ADAS-cog11) score > 12 and a global CDR score of 1 or greater at screening.
3. Patients must have given written informed consent in accordance with GCP and local legislation prior to any study procedures. All patients must be able to give informed consent personally and have capacity for such consent. An informed consent given by a legal representative will not be accepted.
4. Patients must have a reliable study partner (per investigator judgement for instance a family member, partner etc., guardian (must be always the same person)) who is in close contact with the patient, available on call and who is able to contribute to the assessment of the ratings of the functional endpoints including CDR-SB at specific study visits as stated in the [flow chart](#). This person will be able to communicate in the language in which the patient is being assessed and should also serve as a backup contact for the study site. The study partner must sign a separate informed consent form which describes their contributions during the study.
5. Patients must have at least 6 years of formal education and fluency in the test language as verbally confirmed by the patient and documented by the study investigator.
6. Previous use of AD medications (AChEIs, memantine) is allowed up 3 month prior to screening. Patients who are currently taking AChEIs are eligible as long as they have been using a stable dose for at least 3 months prior to screening and no change is foreseen for the duration of the study. This dose must be consistent with the product label in the concerned country. Patients currently taking memantine are excluded. .
7. Male or female patients at least 55 years of age. Patients older than 85 years may be included based on an acceptable general health status, (e.g. concomitant diseases, physical capability to follow the required study procedures [visits etc.]) at discretion of the investigator.

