### **ADCS-ADL**

This is a rating scale used to assess basic and instrumental activities of daily living. In the full version of the scale, 23 items are rated by the investigator using information supplied by the caregiver. Each item has a score range varying from 0-3 to 0-5. The sum score could range from 0 to 78. Higher scores indicate better function [[R97-3207](#)].

**CDR-SB** is obtained through semi structured interviews of patients and informants, and cognitive functioning is rated in 6 domains of functioning: memory, orientation, judgment and problem solving, community affairs, home and hobbies, and personal care. Each domain is rated on a 5-point scale of functioning as follows: 0, no impairment; 0.5, questionable impairment; 1, mild impairment; 2, moderate impairment; and 3, severe impairment (personal care is scored on a 4-point scale without a 0.5 rating available). The CDR-SB score is computed [[R03-0748](#)].

**ADAS-cog/11** is an 11-item cognitive subscale that objectively measures memory, language, orientation and praxis with a total score range of 0 to 70 [[R96-2608](#)].

[REDACTED] has been selected as service provider to support tasks related to the neuropsychological assessments.

The services of [REDACTED] include:

- Necessary Rater prequalification
- Central Rater training for neuropsychological assessments used as primary and secondary endpoints (online and at investigator meeting)
- Provision of Rater materials
- Central Quality Review of Assessments

Details of rater prequalifications, Rater Training, Rater Materials (including Assessments) and of the Central review procedures will be available in a separate document filed in the ISF.

These members of the site staff conducting the neuropsychological assessments have to be adequately trained (either at the investigator training or individually) and training

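### Protocol section 6.2 orders screen failure below a CDR total score greater than 1, while inclusion criterion 2 and the synopsis accept a global CDR of 1 or greater; the rules differ in measure and inequality and must be reconciled

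*Protocol*

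**What the plan says.** Three places in the current protocol state a CDR requirement for entry.

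- **Section 3.3.2, inclusion criterion 2:** besides the MMSE and ADAS-cog11 limits, "a global CDR score of 1 or greater at screening".
- **Synopsis, main criteria for inclusion:** "a global CDR score of 1 or greater are required for inclusion".
- **Section 6.2**, in the text on re-using screening results in the parallel trial 1289.5: patients below the required MMSE or CDR result are to be failed, the CDR part reading "CDR total score of greater than 1 are not eligible for this study and must be registered as screen failure in IRT".

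Section 6.2 does not define the CDR total score as a screening measure. Elsewhere, the synopsis attaches the term total score to the CDR Sum of Boxes. The flow chart lists CDR at screening and CDR-SB only from Visit 3. Section 5.1.2 gives the rating levels for the CDR domains: "0, no impairment; 0.5, questionable impairment; 1, mild impairment; 2, moderate impairment; and 3, severe impairment", with no 0.5 level for personal care.

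Two other places handle the same decision by pointing to the criteria. Section 6.2.1 (Visit 1) has sites review the inclusion and exclusion criteria once results are in, and register as a screen failure anyone who does not meet them. SAP Table 6.2:1, item A1.3, judges an inadequate MMSE, ADAS-cog11 or CDR score against inclusion 2.

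**The concern.** The section 6.2 sentence is a mandatory instruction about a registration step in IRT. A site holding both section 6.2 and section 6.2.1 has two screen-failure rules that can disagree on the same patient. The score at which they may disagree, exactly 1, is the level called mild at box level, and section 6.2 itself says the trial investigates mild Alzheimer's dementia.

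What is at stake is who enters, and whether sites apply the same entry rule. A wrongly failed patient is lost to the trial in most cases, because section 3.3 allows re-screening only exceptionally. The error would also be hard to audit: the list of data collected for screen failures in section 3.3.4.1 does not name the CDR, and SAP item A1.3 refers to inclusion 2 only.

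**Working it through.** The plan states no figure on this point, so there is nothing to reproduce. The check sets the rules side by side and tests each reading of total.

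| Source | Measure | Inequality |
|---|---|---|
| Inclusion 2 | global CDR | ≥ 1 |
| Synopsis | global CDR | ≥ 1 |
| Section 6.2 | CDR total score (undefined) | > 1 |

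**Reading A: total means the global score.** Assumption: the global score takes the five levels that section 5.1.2 gives for the boxes. The documents give neither the levels nor the scoring algorithm of the global score.

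| Score | Inclusion 2 (≥ 1) | Section 6.2 (> 1) |
|---|---|---|
| 0 | fail | fail |
| 0.5 | fail | fail |
| 1 | pass | **fail** |
| 2 | pass | pass |
| 3 | pass | pass |

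The rules differ at exactly one level, 1. A site that applies both must follow the stricter one and fail every patient rated 1.

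**Reading B: total means the Sum of Boxes.** Five boxes take 0, 0.5, 1, 2 or 3, and personal care takes 0, 1, 2 or 3. That gives 5⁵ × 4 = 3,125 × 4 = 12,500 possible patterns, with sums from 0 to 18.

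Patterns that do not exceed 1:
- sum 0: 1 pattern
- sum 0.5: 5 patterns (one of the five boxes at 0.5)
- sum 1: 6 patterns with a single box at 1, plus 10 with two boxes at 0.5, giving 16
- in all 1 + 5 + 16 = 22

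So 12,500 − 22 = 12,478 patterns pass section 6.2. Among them are patterns in which no box is above 0.5: ten with three boxes at 0.5 (sum 1.5), five with four (sum 2.0) and one with five (sum 2.5), 16 in all. These count score patterns, not patients, and say nothing about frequency at screening. They show only that a sum above 1 is a different and much weaker test than one set at the global score.

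Under Reading B, section 6.2 still admits nobody by itself. It gives a reason to fail a patient, and section 3.3.2 requires every inclusion criterion to be met. A patient with three boxes at 0.5 clears section 6.2 and must still satisfy inclusion 2.

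**The rest of the sentence.** Its MMSE limit (<27) agrees with the upper end of the 18–26 range in inclusion 2, but the lower end and the ADAS-cog11 limit are absent. It therefore does not restate the eligibility rule in full.

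**The case against.** The strongest reply is that section 6.2 is a loose paraphrase introducing the re-use of MMSE and CDR results, and that the working rule is in section 6.2.1, which ties screen failure to the inclusion and exclusion criteria. Sections 3.1 and 4.1 tie randomisation to the same criteria. Since the synopsis uses total score for the Sum of Boxes, the less harmful reading is plausible. The harmful reading visibly conflicts with the stated mild population, so sites would probably query it. Much of this stands, and it limits the point.

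A reader might infer more than the documents support:

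- **That the two rules necessarily enrol different populations.** This follows under Reading A. Under Reading B inclusion 2 remains binding, and enrolment differs only if a site applies section 6.2 alone.
- **That patients wrongly failed would never be seen.** Screen failures are recorded in the eCRF, and the screened set feeds the disposition table (SAP section 6.3). They are counted; what may be missing is the CDR result behind the failure. Item A1.3 concerns entry criteria not met and is not meant to detect wrongly failed patients.
- **That the rule sends failed patients to trial 1289.5.** That provision is in the following sentence. It applies only if the results meet that trial's requirements, the patient and study partner agree, and new consent is given.

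What the reply does not remove is a mandatory threshold, in current text, that differs from the inclusion criterion in both measure and inequality. That sites might guess the intent is a reason to correct the sentence.

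**Conclusion.** The contradiction is real and unresolved in the documents. Its consequence depends on an undefined term.

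- If total means global, a site applying both rules fails every patient rated exactly 1, all of whom satisfy the CDR part of inclusion 2. This rests on the assumption that the global score uses the box levels; the label mild for a rating of 1 likewise comes from the box scale.
- If total means Sum of Boxes, section 6.2 is looser and inclusion 2 governs, so harm is confined to sites using section 6.2 alone.

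The number of patients affected cannot be derived, because the documents give no distribution of CDR scores at screening and no indication of how sites read the sentence. The effect is on who is enrolled; nothing here alters the randomised comparison, the alpha level or the power calculation. The point is an inconsistency of wording in an operational rule, not a fault of design.

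**What to change.** Reconcile the synopsis, inclusion criterion 2 and section 6.2 on one CDR measure and one inequality. Which rule is intended is for the sponsor to confirm. The simplest edit is to remove the thresholds from section 6.2 and refer to the inclusion criteria, as section 6.2.1 and SAP item A1.3 already do. That also removes the partial MMSE limit and the missing ADAS-cog11 limit. Sites should be notified of the correction. The cost is one sentence of protocol text and a site notice, with no added patients or procedures.

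Separately, as a minor wording point: section 3.3 still describes those to be randomised as "Untreated male and female patients, at least 55 years old". Inclusion 6 admits patients on a stable AChEI dose, and section 7.5 stratifies by current AChEI use. The word should be reconciled with those sections in the same revision. It has no bearing on the CDR threshold.

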### 6.2.1 Screening and run-in period(s)

#### Visit 1 (screening)

- Patients must sign Informed Consent ( [REDACTED] ) before any study related procedures are performed.
- The patient should be recorded on the enrolment log and be registered in the IRT as a screened patient.
- Study procedures have to be completed according to the [Flow Chart](#).
- Demographics include age, educational level, current or past professional experience
- ECG and vital sign measurement will be performed.
- For diabetic patients with antidiabetic therapy: exclusion of hypoglycemia for the period of the neuropsychological assessment (documented plasma glucose concentration  $\geq 90$  mg/dl (5mmol/l) at the beginning and directly after the assessment). If glucose is too low patients need to eat a snack and then be retested to confirm that the blood sugar value is above 90 mg/dl before the tests are started
- Blood pressure must always be measured before taking any blood sample.
- A complete physical examination and neurological examination.
- Laboratory samples will be collected as described in the flow chart.
- Assessment for MRI (if no pre-existing MRI or CT of the brain is already available (please refer to [inclusion criteria](#) for details)) must be scheduled in order that results are available prior to Visit 2
- Administer the following neuropsychological assessments in the following order:

Proprietary confidential information.

© 2017 Boehringer Ingelheim International GmbH or one or more of its affiliated companies. All rights reserved.

This document may not - in full or in part - be passed on, reproduced, published or otherwise used without prior written permission.

- MMSE
- CDR
- ADAS-cog11
- Administration of C-SSRS (baseline/screening scale)
- Once Visit 1 procedures are complete and laboratory results are received, inclusion/exclusion criteria must be reviewed again. If the patient is still eligible according to inclusion/exclusion criteria, the patient should be contacted to schedule next visit.
- If a patient does not meet inclusion/exclusion criteria the patient must be recorded in CRFs as a screen failure. Patient must be registered as screen failure in IRT.

